13.2.4 Access to Records

The investigator will make the office and/or hospital records of subjects enrolled in this study available for inspection by Vertex or its representative at the time of each monitoring visit and for audits. The records will also be available for direct inspection, verification, and copying, as required by applicable laws and regulations, by officials of the regulatory health authorities (FDA and others). The investigator will comply with applicable privacy and security laws for use and disclosure of information related to the research set forth in this protocol.

13.2.5 Subject Privacy

To maintain subject confidentiality and to comply with applicable data protection and privacy laws and regulations, all eCRFs, study reports, and communications relating to the study will identify subjects by assigned subject numbers and access to subject names linked to such numbers shall be limited to the site and the study doctor and shall not be disclosed to Vertex. As required by applicable laws and regulations in the countries in which the study is being conducted, the investigator will allow Vertex and/or its representatives access to all pertinent medical records to allow for the verification of data gathered in the eCRFs/SAE forms and the review of the data collection process. The FDA and regulatory authorities in other jurisdictions, including the IRB/IEC, may also request access to all study records, including source documentation, for inspection.

For sites participating in the study in the US, and in accordance with the Health Insurance Portability and Accountability Act and associated regulations (“HIPAA”) an executed HIPAA authorization shall be obtained by the site from each subject (or the legal representative of the subject) before research activities may begin. Each HIPAA authorization shall comply with all HIPAA requirements including authorization allowing the site access to and use of the subject’s personally identifiable health information, authorization for the site to disclose such information to Vertex, the FDA and other parties requiring access under the Protocol, and statements as to the purpose for which such information may be used and for how long.

13.2.6 Record Retention

The investigator will maintain all study records according to ICH GCP guidelines and/or applicable local regulatory requirement(s), whichever is longest, as described in the Clinical Trial Agreement. If the investigator withdraws from the responsibility of keeping the study records, custody will be transferred to a person willing to accept the responsibility and Vertex will be notified.

13.2.7 Study Termination

At any time, Vertex may terminate this study in its entirety or may terminate this study at any particular site. In addition, for reasonable cause, either the investigators or their IRBs/IECs may terminate the study at their center.

Conditions that may lead to reasonable cause and warrant termination include, but are not limited to:

- Subject or investigator noncompliance
- Unsatisfactory subject enrollment
- Lack of adherence to protocol procedures
- Lack of evaluable and/or complete data
- Potentially unacceptable risk to study subjects
- Decision to modify drug development plan
- Decision by the FDA or other regulatory authority

Written notification that includes the reason for the clinical study termination is required.

13.3 Data Quality Assurance

Vertex or its designated representative will conduct a study site visit to verify the qualifications of each investigator, inspect clinical study site facilities, and inform the investigator of responsibilities and procedures for ensuring adequate and correct study documentation.

The investigator is required to prepare and maintain adequate and accurate case histories designed to record all observations and other data pertinent to the study for each study participant. Study data for each enrolled subject will be entered into an eCRF by study site personnel using a secure, validated web-based electronic data capture (EDC) application. Vertex will have read-only access to site-entered clinical data in the EDC application.

Instances of missing, discrepant, or uninterpretable data will be queried with the investigator for resolution. Any changes to study data will be made to the eCRF and documented in an audit trail, which will be maintained within the clinical database.

13.4 Monitoring

Monitoring and auditing procedures developed or approved by Vertex will be followed to comply with GCP guidelines. On-site checking of the eCRFs/SAE Forms for completeness and clarity, cross-checking with source documents, and clarification of administrative matters will be performed.

The study will be monitored by Vertex or its designee. Monitoring will be done by personal visits from a representative of Vertex, or designee (study site monitor), who will review the eCRFs/SAE Forms and source documents. The study site monitor will ensure that the investigation is conducted according to the protocol design and regulatory requirements.

13.5 Electronic Data Capture

Vertex will provide the study sites with secure access to and training on the EDC application sufficient to permit study site personnel to enter or correct information in the eCRFs on the subjects for which they are responsible.

An eCRF will be completed for each enrolled study subject. It is the investigator's responsibility to ensure the accuracy, completeness, clarity, and timeliness of the data reported in the subject's eCRF. Source documentation supporting the eCRF data will indicate the subject's participation in the study and will document the dates and details of study procedures, AEs, other observations, and subject status.

The investigator, or designated representative, will complete the eCRF as soon as possible after information is collected.

The audit trail entry will show the user's identification information and the date and time of any correction. The investigator will provide formal approval of all the information in the eCRFs, including any changes made to the eCRFs, to endorse the final submitted data for the subjects for whom the investigator is responsible.

Vertex will retain the eCRF data and corresponding audit trails. A copy of the final archival eCRF in the form of a CD or other electronic media will be placed in the investigator's study file.

13.6 Publications and Clinical Study Report

13.6.2 Clinical Study Report

A clinical study report, written in accordance with the ICH E3 Guideline, will be submitted in accordance with local regulations.

3 INTRODUCTION

Study VX14-661-110 (Study 110) is a Phase 3, Open-label, rollover study to evaluate the safety and efficacy of long-term treatment with VX-661 in combination with ivacaftor (IVA) in subjects aged 12 years and older with cystic fibrosis, homozygous or heterozygous for the *F508del-CFTR* mutation.

This SAP will focus on the safety and efficacy analysis for all the subjects enrolled in Part A. As there is no subject enrolled in Part A Observational Cohort, the methods pertain to Part A Treatment Cohort, unless specified otherwise.

The Vertex Biometrics department or a designated Contract Research Organization (CRO) will perform the statistical analysis of the safety and efficacy data. SAS[®] Version 9.4 Software (SAS Institute, Cary, North Carolina, USA) or higher will be used to generate all statistical outputs (tables, figures, listings, and datasets). This SAP will be finalized and approved prior to the final clinical data lock.

4 STUDY OBJECTIVES

4.1 Primary Objective

Part A

To evaluate the long-term safety and tolerability of VX-661/IVA in subjects with CF, homozygous or heterozygous for the *F508del-CFTR* mutation who are in the Treatment Cohort

4.2 Secondary Objectives

Part A

Treatment Cohort

To evaluate the long-term efficacy of VX-661/IVA for subjects in the Treatment Cohort

Observational Cohort

To evaluate the post-treatment safety of VX-661/IVA for subjects in the Observational Cohort

5 STUDY ENDPOINTS

5.1 Primary Endpoints

Part A

Treatment Cohort

Safety and tolerability of long-term treatment of VX-661/IVA based on adverse events (AEs), ophthalmologic exams (subjects <18 years of age [age on the date of informed consent/assent in the parent study]), clinical laboratory values (serum chemistry, hematology, coagulation, lipids, vitamins, and urinalysis), standard digital electrocardiograms (ECGs), vital signs, and pulse oximetry.

5.2 Secondary Endpoints

Part A

Treatment Cohort

- Absolute change from baseline in percent predicted forced expiratory volume in 1 second (ppFEV₁)
- Relative change from baseline in ppFEV₁
- Number of pulmonary exacerbations (PEX)
- Absolute change from baseline in body mass index (BMI)
- Absolute change from baseline in BMI z-score for subjects aged <20 years
- Absolute change from baseline in Cystic Fibrosis Questionnaire–Revised (CFQ-R) respiratory domain score
- Absolute change from baseline in body weight
- Absolute change from baseline in body weight z-score for subjects aged <20 years
- Absolute change from baseline in height z-score for subjects aged <20 years
- Time-to-first PEX
- Pharmacokinetic (PK) parameters of VX-661, a VX-661 metabolite (M1-661), IVA, and an IVA metabolite (M1-IVA)

Observational Cohort

- Safety, as determined by related serious adverse events (SAEs)

6 STUDY DESIGN

6.1 Overall Design

This is a Phase 3, multicenter, open-label, rollover study in subjects with CF who are homozygous or heterozygous for the *F508del-CFTR* mutation and who participated in Studies VX13-661-103 (Study 103), VX14-661-106 (Study 106), VX14-661-107 (Study 107), VX14-661-108 (Study 108), VX14-661-109 (Study 109), VX14-661-111 (Study 111), Study 112, VX16-661-114 (Study 114), or other Vertex studies investigating VX-661/IVA. The study is designed to evaluate the safety and efficacy of long term treatment of VX-661/IVA.

A schematic of the study design is shown in [Figure 6-1 Study Design](#).

Part A

Part A consists of a Treatment Cohort and an Observational Cohort (see definitions below). Subjects from Studies 103, 106, 107, 108, 109, 111, and other eligible Vertex studies investigating VX-661/IVA, may enroll in Part A. The Treatment Cohort and the Observational Cohort will be open to enrollment in parallel. The analyses specified in this SAP focus on the Part A Treatment Cohort only.

Treatment Cohort

Subjects who completed study drug treatment (i.e., VX-661/IVA, IVA monotherapy, or placebo) during the Treatment Period in the parent study who meet the eligibility criteria (Study Protocol Sections 9.1 and 9.2) will be offered the opportunity to enroll in Study 110. Subjects who permanently discontinue study drug treatment or who withdrew consent during the parent studies are not eligible for enrollment in the Treatment Cohort.

Subjects in the Treatment Cohort will receive VX-661 100 mg/IVA 150-mg fixed-dose combination (FDC) tablet daily (qd) in the morning and IVA 150-mg tablet qd in the evening. The Treatment Period will be approximately 96 weeks.

[figure not shown]
Subjects may screen for another qualified Vertex study while participating in the Treatment Cohort. Subjects who completed at least 4 weeks of treatment before discontinuing Study 110 to participate in another qualified Vertex study, and who meet the eligibility criteria (Study Protocol Sections 9.1 and 9.2), will be offered the opportunity to re-enroll in the Treatment Cohort of Study 110. Subjects who re-enroll will resume treatment with VX-661/IVA at the next study day after their previous treatment discontinuation from Study 110 (e.g., a subject who discontinued at Study Day 50 would resume treatment at Study Day 51). Subjects who discontinue Study 110 more than once to participate in another qualified Vertex study may not re-enroll in Study 110 a second time.

Observational Cohort

Subjects <18 years of age (age on the date of informed consent/assent in the parent study) who received at least 4 weeks of study drug in the parent study, who are not eligible for the Treatment Cohort or who elect not to enroll in the Treatment Cohort, and meet eligibility criteria (Study Protocol Section 9.1) will be offered the opportunity to enroll in the Observational Cohort.

Subjects in the Observational Cohort will not receive study drug and will have regularly scheduled telephone calls for approximately 2 years after their last dose of study drug in the parent study to assess post-treatment safety of VX-661/IVA combination therapy.

Figure 6-1 Study Design

ivacaftor; q12h: every 12 hours; qd: daily.

Notes: All subjects will receive a VX-661 100 mg/ivacaftor 150-mg fixed dose combination tablet qd in the morning and an ivacaftor 150-mg tablet qd in the evening.

- a Subjects enrolled in parent studies may be eligible to enroll in the Part A Treatment Cohort or Part B if they completed study drug treatment in the parent study and meet the eligibility criteria for the Part A Treatment Cohort or Part B. Subjects who complete Part A of Study VX14-661-110 may continue into Part B of the study.
- b Subjects may be eligible to re-enroll in the Part A Treatment Cohort or Part B if they completed the last required visit of another qualified Vertex study and meet eligibility criteria for re-enrollment.
- c Subjects who re-enroll in the Part A Treatment Cohort or in Part B will complete the Returning Visit and resume treatment with VX-661/IVA on the next study day after their previous treatment discontinuation from Study VX14-661-110.
- d The Safety Follow-up Visit in the Part A Treatment Cohort is scheduled to occur 28 (\pm 7 days) after the last dose of study drug in Part A (Section 8.1.1.2) for subjects who do not enroll in Part B. The Safety Follow-up Visit in Part B is scheduled to occur 28 (\pm 7 days) after the last dose of study drug in Part B. Exceptions are explained elsewhere in the protocol.
- e During the course of study conduct, if VX-661 in combination with ivacaftor is approved and available for the treatment of CF in populations enrolled in Study VX-661-110, subjects with the approved *CFTR* genotypes may be discontinued from this rollover study at the discretion of the sponsor. If a subject is continuing onto commercially available VX-661/ivacaftor, the Early Treatment Termination Visit will be completed before dosing with commercial drug begins, and the Safety Follow-up Visit will not be required. Alternatively, if local health authorities decline to approve, or if clinical benefit is not demonstrated for the use of VX-661 in combination with ivacaftor for the treatment of CF in populations enrolled in Study VX-661-110, subjects with the relevant *CFTR* genotypes may be discontinued after communication to investigators and IRBs/IECs of the risks/benefits related to the safety and efficacy observed for the subset of subjects. If subjects are discontinued from the study, an Early Treatment Termination Visit should occur within 7 days of the last dose of study drug and a Safety Follow-up Visit should occur within 28 (\pm 7) days after the last dose of study drug.
- f Subjects <18 years of age (age on the date of informed consent/assent in the parent study) who are not eligible for the Treatment Cohort, or elect not to enroll in the Treatment Cohort, may be eligible for the Observational Cohort.
- g A telephone contact will be made every 3 to 4 months during the first year and at approximately 2 years (\pm 4 weeks).

6.2 Sample Size and Power

Part A

Treatment Cohort

1,044 eligible subjects are enrolled from the following parent studies:

- 23 subjects from Study 103.
- 464 subjects from Study 106.
- 159 subjects from Study 107.

- 227 subjects from Study 108.
- 138 subjects from Study 109.
- 33 subjects from Study 111.

Observational Cohort

No patient enrolled in observational cohort.

6.3 Randomization

Randomization is not required because all subjects will receive the same open-label active study drug in the Treatment Cohort.

6.4 Blinding and Unblinding

This will be an open-label study. However, subjects should not be informed of their study-related spirometry results during the study regardless of whether the subject has prematurely discontinued treatment.

7 ANALYSIS SETS

The **All Subjects Set** is defined as all subjects who have signed informed consent (enrolled) or have received at least 1 dose of study drug in Part A. This analysis set will be used in subject data listings and disposition summary tables, unless otherwise specified.

7.1 Efficacy Analysis Sets

The **Full Analysis Set (FAS)** is defined as all enrolled subjects who have received at least 1 dose of study drug in Part A and have one of the following mutations: *F508del/F508del (F/F)* and *F508del/Residual function (F/RF)*. The FAS is to be used in the efficacy analyses unless otherwise specified.

Study 106 and 108 were the basis for the approval of TEZ/IVA. Although Study 107 and 109 subjects were rolled over to FAS in Study 110, after the study results were available, subjects from Study 107 and 109 were early discontinued from Study 110. Thus, the efficacy analysis will focus on the **106/110 Efficacy Set (ES)** and **108/110 ES**, defined as all the FAS subjects rolling over from Study 106 and 108 respectively.

As shown in [Table 7-1](#), treatment group assignment is based on the randomized treatment in parent study. For 108/110 ES, the randomized treatment assignment in Period 2 will be used to assign subjects to a treatment group in Study 110.

Treatment Group	Description
TEZ/IVA	Subjects randomized to TEZ/IVA in parent study
PBO-TEZ/IVA	Subjects randomized to placebo in parent study
IVA-TEZ/IVA	Subjects randomized to IVA in parent study

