12.2 Analysis Sets

For subjects in the Treatment Cohort, the assignment to analysis sets will be done before the clinical data lock for the study.

The All Subjects Set is defined as all subjects who signed informed consent (enrolled) and have received at least 1 dose of study drug in Study VX14-661-110. This analysis set will be used in subject listings and disposition summary tables unless otherwise specified.

The Full Analysis Set (FAS) is defined as all enrolled subjects who have received at least 1 dose of study drug in Study VX14-661-110 and have one of the following mutations: *F508del/F508del*, *F508del/Residual function*, and *F508del/Gating*. The FAS is to be used in the efficacy analyses unless otherwise specified.

The Safety Set is defined as all subjects who received at least 1 dose of study drug in Study VX14-661-110. The Safety Set is to be used for the safety analyses unless otherwise specified.

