12.3.4 Efficacy Analysis

Treatment Cohort

Assessment of the long-term efficacy and tolerability of VX-661 /ivacaftor for subjects in the Treatment Cohort is a secondary or other objective of this study. The efficacy analysis will be performed on each CFTR mutation group separately (*F508del/F508del*, *F508del/Residual function*, and *F508del/Gating*). All data collected during the efficacy analysis period through the end of Study VX14-661-110 will be summarized.

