9.6.2 Analysis of Efficacy Endpoints

Most continuous endpoints during 110 Efficacy Analysis Period will be analyzed for subjects in 106/110 ES and 108/110 ES using a mixed-effects model for repeated measures (MMRM) with similar specification as in the parent study SAP/CSR, if applicable. However, these MMRM analysis will be restricted to the last visit at which the total number of subjects is approximately 70% of subjects from the respective parent study.

These continuous endpoints during 110 Efficacy Analysis Period will also be descriptively summarized for subjects in FAS who roll over from Study 103 and 111, where the patients carry *F/F* mutation.

No hypothesis testing will be done for between-group comparisons.

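### The SAP omits F508del/Gating from the Full Analysis Set, contradicts itself on whether Study 107 and 109 subjects belong to that set, and plans no efficacy summary for them

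*SAP*

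**What the plan says.** Protocol 12.2 defines the FAS as "enrolled subjects who have received at least 1 dose of study drug in Study VX14-661-110 and have one of the following mutations", and then lists three genotypes: F508del/F508del (F/F), F508del/residual function (F/RF) and F508del/Gating. On the efficacy analysis, Protocol 12.3.4 says: "The efficacy analysis will be performed on each CFTR mutation group separately". It names the same three groups and adds that all data from the efficacy analysis period are to be summarized. The synopsis and Protocol 12.3.2 repeat the three-group commitment.

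SAP 7.1 keeps the form of the definition but lists only F/F and F/RF. Its next paragraph begins: "Although Study 107 and 109 subjects were rolled over to FAS in Study 110, after the study results were available". It goes on to say that these subjects were discontinued early from Study 110, and concludes that efficacy will focus on rollovers from Studies 106 and 108, which it describes as the basis for approval.

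SAP 9.6.2 applies the repeated-measures model to the 106/110 and 108/110 efficacy sets. Outside those sets, continuous endpoints are only "descriptively summarized for subjects in FAS who roll over from Study 103 and 111". The exacerbation sets in SAP 7.2 are built from Studies 106 and 108 alone. No efficacy section covers Study 107 or 109.

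**The concern.** A genotype group that the protocol places in the FAS, with an efficacy analysis of its own, is absent from the SAP's FAS. The SAP text refers to parent-study results and to the approval as past events, so the narrowing was written with those results in hand. The reason it gives, early discontinuation, is attached to the focus on Studies 106 and 108. Nothing is said about why F/Gating leaves the FAS definition.

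Two things are at stake. First, long-term efficacy would be reported for some of the genotypes the protocol named and not for another, and a reader of the study report could not see what the omitted group showed before it stopped. Second, SAP 9.2 tabulates the FAS in the disposition table, and SAP 7.1 supports two different readings of who is in it.

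**Working it through.** **Inputs (SAP 6.2).** The plan's total is "1,044 eligible subjects are enrolled from the following parent studies". The components are "23 subjects from Study 103", "464 subjects from Study 106" and "159 subjects from Study 107", with 227 from Study 108, 138 from Study 109 and 33 from Study 111.

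**The plan's own figure.** 23 + 464 + 159 + 227 + 138 + 33 = 1,044. The stated total is reproduced.

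**Who gets an efficacy summary under SAP 9.6.2**

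| Parent study | n | Planned efficacy output |
|---|---|---|
| 106 | 464 | Model and descriptive |
| 108 | 227 | Model and descriptive |
| 103 | 23 | Descriptive |
| 111 | 33 | Descriptive |
| 107 | 159 | None |
| 109 | 138 | None |

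- Some summary: 464 + 227 + 23 + 33 = 747; 747 / 1,044 = 71.6%.
- None: 159 + 138 = 297; 297 / 1,044 = 28.4%.
- Descriptive only: 23 + 33 = 56.

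**Where F/Gating subjects can be.** Protocol 8.2.1 describes Studies 103, 106 and 111 as homozygous, and Studies 107, 108 and 109 as heterozygous without naming the second allele. SAP 9.6.2.2.2 adjusts the Study 108 exacerbation model for residual-function mutation class, which identifies Study 108 as the residual-function study. All 1,044 subjects come from these six studies, so any F/Gating subjects come from Study 107 or 109.

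**Size of the F/Gating group (assumption).** If one of the two studies consists of F/Gating subjects and the other has none:

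- Study 109: 138 / 1,044 = 13.2%.
- Study 107: 159 / 1,044 = 15.2%.

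**FAS count under each reading.** This assumes that every enrolled subject was dosed and that no Study 107 or 109 subject carries a residual-function mutation.

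- SAP definition: 747.
- Protocol definition: 747 + 138 = 885, or 747 + 159 = 906, under the same one-study assumption.
- SAP sentence taken literally: 747 + 297 = 1,044.

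**Does early discontinuation rule out a descriptive table?** SAP 9.6.2 restricts the model to visits that retain about 70% of parent-study subjects, but sets no such threshold for descriptive summaries. SAP 11.1 maps early-termination assessments into the regular visit windows. Whatever visits these subjects reached can therefore be tabulated with n per visit. Group size is no obstacle either: 138 or 159 is larger than the 23 and 33 that do get tables.

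**The case against.** The best case for the SAP has five parts.

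- **The stated reason is not the results themselves.** The quoted sentence goes on to say that Study 107 and 109 subjects were discontinued early, and the focus on Studies 106 and 108 follows from that. Protocol 8.1, 8.2.1 and 10.6 foresaw stopping genotype groups without demonstrated benefit or approval, and 8.2.1 reports that Study 107 met futility criteria. A reader might infer that the group was removed because of its results. The documents do not support that: they show timing, not motive. Yet the protocol that foresaw these discontinuations still kept F/Gating in the FAS, so they do not explain the changed definition.
- **The 28.4% is not the F/Gating group.** A reader might take it that way, but it pools two studies. If one of them enrolled none of the three protocol genotypes, the protocol's own FAS leaves that study out too. Nor do the documents say which of the two is the gating study. This stands.
- **The SAP has one explicit definition, and the conflicting sentence is background.** A programmer would probably apply the definition. That makes the contradiction easy to correct, but it is still there.
- **Studies 103 and 111 differ.** They are F/F, fall within the SAP's FAS, and are not reported as stopped as a group. True, but this explains their inclusion under the narrowed definition, not the narrowing.
- **Document versions may differ.** The SAP assumes a Part A and Part B that the supplied protocol does not have, so it may follow another protocol version with a different FAS. Departure from the governing version is therefore not proven. The mismatch between the two supplied documents, and the inconsistency inside SAP 7.1, do not depend on it.

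**Conclusion.** The point holds as one of incomplete and inconsistently defined efficacy reporting, set down after parent-study results were known. The omission of F/Gating, the conflict within SAP 7.1 and the absence of any efficacy summary for the 297 Study 107 and 109 subjects can all be read directly from the documents. The size of the F/Gating group cannot. The figures of 13.2% and 15.2% rest on the assumption that the group is exactly one of the two studies, and all percentages use enrolled subjects because the number dosed is not given separately.

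The consequence is bounded. Efficacy is a secondary objective, and SAP 9.6.2 rules out between-group testing, so no type I error is involved. Safety, the primary objective, is unaffected: the Safety Set in SAP 7.3 ignores genotype, and SAP 9.7.1 includes parent-study adverse event tables for Studies 107 and 109. The change should be made, but it does not threaten the study's main conclusion.

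**What to change.** - In SAP 7.1, restore F508del/Gating to the FAS in line with Protocol 12.2.
- For FAS subjects with F508del/Gating, whichever parent study they came from, add the by-visit descriptive summaries already specified in SAP 9.6.2.1.3, 9.6.2.1.4 and 9.6.2.4.2, through the last visit reached and with n at each visit.
- Keep the repeated-measures models limited to the 106/110 and 108/110 efficacy sets.
- Correct the sentence that places Study 107 and 109 subjects in the FAS, so that the FAS count in the disposition table has a single definition.

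This need not bring all 297 subjects into an efficacy table. Any Study 107 or 109 subject with none of the three protocol genotypes would stay outside the FAS under the protocol as well.

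The cost is one more set of descriptive tables from data already collected. The tables will show short and shrinking follow-up, and the n per visit makes that visible.
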